## 3. STUDY DESIGN

### 3.1. Design

Clinical study BCD-066-3 was a double-blind controlled, randomized, parallel-group study of the pharmacokinetics, pharmacodynamics, tolerability, and safety of repeated-dose intravenous BCD-066 and Aranesp®.

The study was planned to include 62 healthy male volunteers (56 active participants and 6 back up subjects to replace dropouts). Before inclusion in the study, all potential participants are

given full information about the study. This information is presented in the Participant Information Sheet. If the potential participant gives his consent to be in the study, he has to sign the Informed Consent Form for participation in a clinical study and then undergo a 14-day screening examination to confirm that he is eligible for the study.

After passing the screening and being considered eligible for the study, subjects are centrally randomized at a 1:1 ratio to one of two treatment groups (#1 and #2).

- Subjects in Group #1 will receive IV injections of 1.0 µg/kg BCD-066 on Day 1, Day 8, Day 15, and Day 22.
- Subjects in Group #2 will receive IV injections 1 µg/kg Aranesp® on Day 1, Day 8, Day 15, and Day 22.

This is a double blind study, which means that neither the investigator nor the subject will know what drug is used in each group.

Blood samples for evaluation of darbepoetin alfa concentration will be collected 30 min, 20 min, and 10 min before the injection, immediately before the injection (not more than 5 min before drug administration), and then 5 min, 10 min, 15 min, 20 min, 30 min, 45 min, 1 h, 2 h, 4 h, 8 h, 16 h, 24 h, 48 h, and 72 h after the first and the fourth IV injection. There will be 4 blood collections before and 14 blood collections after the first and the fourth IV injection of darbepoetin alfa. The serum concentrations will be used to calculate the key PK parameters of darbepoetin alfa. Before the second and the third injection, blood samples will be collected only once. During the entire study, there will be 38 blood collections for PK evaluation.

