### **3.3. Selection of Study Population**

#### **1.3.1. Inclusion criteria**

1. Signed informed consent form
2. Men from 18 to 45 years old (inclusive)
3. BMI within the normal limits (18.5 to 30 kg/m^2)
4. Hemoglobin from 120 g/L to 150 g/L and hematocrit 41% to 49% at screening (before the first injection)
5. Serum transferrin 2.15 g/L to 3.6 g/L; serum ferritin from 20 µg/L to 250 µg/L
6. Vitamin B12 from 187 pcg/mL to 883 pcg/mL; folic acid from 3.1 ng/mL to 20.5 ng/mL
7. Endogenous serum erythropoietin < 30 mIU/mL at screening
8. The subject is verified as “Healthy” according to results of standard clinical, laboratory and instrumental tests
9. Subject’s ability (in the investigator’s opinion) to follow the protocol procedures

10. The subject and his sexual partner with retained childbearing potential consent to implement reliable contraceptive methods starting 2 weeks before inclusion in the study and up to 2 weeks after the last dose of the test/reference drug. This requirement does not apply to surgically sterile subjects. Reliable contraception methods mean one barrier method in combination with one of the following: spermicides, intrauterine device and/or oral contraceptives used by the subject's partner.
11. The subject agrees not to drink alcohol for 24 h prior to each injection of the test/reference drug and for 72 h after the injection.

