### **8.2. Description of the Statistical Methods to be Employed**

#### **Quantitative Data**

The following quantitative data will be analyzed in the study:

Pharmacokinetics:

- Plasma concentration of drug,
- Area under plasma concentration curve,
- Time (e.g., maximum plasma concentration time, half-life)
- Elimination parameters (e.g. clearance, terminal rate constant)

Safety:

- RBC results,
- Blood chemistry results,
- Vital signs;
- ECG findings,
- Urea analysis results,
- Skin disorders size at the sites of venipuncture,

- Skin disorders lifetime at the sites of venipuncture.

Pharmacodynamics:

- Absolute reticulocyte count.
- Hb level.
- Area under effect curve «absolute reticulocyte count — time».
- Area under effect curve «Hb level — time».
- Time (e.g. the time of the maximum increase of absolute reticulocyte count vs. baseline). The

statistical analysis will include two-tailed hypothesis testing; the chosen significance level is 0.05. Quantitative variables will be tested for normality using the Shapiro-Wilk test.

Normally distributed quantitative variables will be tested using the two-sample Student's t-test, Welch's t-test, and ANOVA.

Non-normally distributed quantitative variables will be tested using the Mann-Whitney U-test, the Wilcoxon test, the Kruskal-Wallis test, and the Friedman test.

Normally distributed quantitative data will be described using the following descriptive statistics: mean, SD, CV, min, and max.

Non-normally distributed quantitative data will be described using the following descriptive statistics: median, quartiles, CV, min, and max.

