#### 8.4. Multivariate Comparison

Pharmacokinetic parameters

Based on determined concentrations in blood a number of the pharmacokinetic parameters will be calculated for the study drug:

1.  $C_{max}$  – maximum plasma concentration after the first and the fourth intravenous administration
2.  $T_{max}$  - time until  $C_{max}$  is reached
3.  $AUC_{(0-72)}$  – area under the plasma concentration curve from administration to 72 h after the first and the fourth intravenous administration.

$$AUC_{(0-72)} = \sum_{p=2}^{15} \frac{(C_p + C_{p-1}) * (t_p - t_{p-1})}{2},$$

где  $C_p$  plasma concentration at the moment  $t_p$  (hours);

$t_p \in \{ 0; 0.083; 0.167; 0.25; 0.33; 0,5; 0.75; 1; 2; 4; 8; 16; 24; 48; 72 \}; p=1, \dots, 15$

4.  $AUMC_{(0-72)}$  - the total area under the plasma concentration curve from administration to 72 h after the first and the fourth intravenous administration.

$$AUMC_{(0-72)} = \sum_{p=2}^{15} \frac{(C_p * t_p + C_{p-1} * t_{p-1}) * (t_p - t_{p-1})}{2},$$

где  $C_p$  – plasma concentration at the moment  $t_p$  (hours),

$t_p \in \{ 0; 0.083; 0.167; 0.25; 0.33; 0,5; 0.75; 1; 2; 4; 8; 16; 24; 48; 72 \}; p=1, \dots, 15$

5. Total clearance (CL) will be calculated as:

$$CL = \frac{DOSE}{AUC_{0-72}}$$

6. Mean Residence Time (MRT) will be calculated as:

$$MRT = \frac{AUMC_{0-72}}{AUC_{0-72}}$$

7. Apparent volume of distribution ( $V_d$ ) will be calculated as:

$$V_d = CL * MRT$$

8. Elimination rate constant ( $K_{el}$ ) will be calculated as:

$$k_{el} = \frac{1}{MRT}$$

9. Plasma concentration half-life ( $T_{1/2}$ ) will be calculated as:

$$T_{1/2} = \frac{\ln(2)}{k_{el}} = \ln(2) * MRT$$

10. Area under the plasma concentration curve from 0 to infinity ( $AUC_{(0-\infty)}$ ) will be calculated as:

$$AUC_{(0-\infty)} = AUC_{(0-72)} + \frac{C_{72}}{k_{el}}, \text{ где}$$

$C_{72}$ - plasma concentration of the drug during the 72 hours after the administration of the drug

11. The residual area will be calculated as:

$$\frac{AUC_{(0-\infty)} - AUC_{(0-72)}}{AUC_{(0-\infty)}}$$

Pharmacodynamics parameters

Based on determined hemoglobin level, reticulocytes counts, RBC counts, hematocrit a number of the pharmacodynamics parameters will be calculated for the study drug:

1.  $E_{max}$  – the maximum hemoglobin level (reticulocytes, RBC, hematocrit)
2.  $T_{max}$  - the time to the absolute maximum increase of hemoglobin level ( $E_{max}$ ) (reticulocytes counts, RBC, hematocrit)

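### SAP 8.4 derives half-life from a mean residence time cut off at 72 h, which caps T1/2 at about 25 h and residual area at about one third

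*SAP*

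**What the plan says.** SAP 8.4 integrates concentration (item 3) and concentration times time (item 4) by linear trapezoids on a 15-point grid from 0 to 72 h. The later items build on these two areas:

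- Item 5, "Total clearance (CL) will be calculated as": Dose/AUC(0-72).
- Item 6, "Mean Residence Time (MRT) will be calculated as": AUMC(0-72)/AUC(0-72), with no extrapolated part.
- Item 8, "Elimination rate constant": 1/MRT. Item 9 then gives T1/2 = ln2·MRT.
- Item 10, "Area under the plasma concentration curve from 0 to infinity": AUC(0-72) + C72/k_el.
- Item 11, "The residual area will be calculated as": the share of AUC(0-inf) that lies beyond 72 h.

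T1/2, k_el, residual area, CL and AUC to infinity are listed PK endpoints in SAP 4.1. The protocol's PK Endpoints list them too, but there the area to infinity carries the label AUC0-168.

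On sampling, SAP 3.1 says: "There will be 4 blood collections before and 14 blood collections after the first and the fourth IV injection of darbepoetin alfa". The item 3-4 grid starts at time 0, so no formula uses the 30, 20 and 10 min pre-dose samples. The sample taken just before dose 2 (Day 8, 168 h after dose 1; SAP 3.2) is not used in any of these formulas either.

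**The concern.** The identity k = 1/MRT holds for one-compartment bolus decline when both areas run to infinity. Over 0-72 h, MRT is only a concentration-weighted average of times inside that window, so a long half-life cannot show itself. Section 8.4 is also inconsistent within itself: items 10-11 allow for exposure beyond 72 h, items 5-9 assume there is none, and item 10 then sizes the tail with the k_el from item 8.

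At stake is the accuracy of five reported PK endpoints. Residual area matters most, because its purpose is to show whether 72 h of sampling captured enough exposure, and this formula cannot return more than about one third. Between-product half-life ratios are also pulled toward 1, which is an unwelcome direction in a comparison of two products.

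**Working it through.** The plan states no T1/2, MRT or residual-area figure, so there is none to reproduce.

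**Inputs.** From SAP 8.4: t = 0, 0.083, 0.167, 0.25, 0.33, 0.5, 0.75, 1, 2, 4, 8, 16, 24, 48, 72 h, with linear trapezoids. Assumed: the true half-life; C = exp(-kt) with C0 = 1; time-0 value zero before background (it is a pre-dose sample); background either none or a constant 1% of C0.

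**Ceilings (no half-life needed).** MRT = Σ(w·C·t)/Σ(w·C), with trapezoid weights w.

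- If C never rises with t, the Chebyshev sum inequality gives MRT ≤ Σ(w·t)/Σw = 2592/72 = 36 h.
- So T1/2 ≤ 36 × 0.6931 = 24.95 h.
- For such a profile AUC(0-72) ≥ 72·C72, and the tail C72·MRT ≤ 36·C72. So residual area ≤ 36/(72 + 36) = 33.3%.
- With a zero at time 0 and a flat profile from 5 min, the values are 36.02 h, 24.97 h and 33.4%.
- A true half-life of 1000 h would read 24.7 h.

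**One case in full: true T1/2 25 h, no background.**

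- AUC(0-72) = 31.67; AUMC(0-72) = 754.3; MRT = 754.3/31.67 = 23.82 h; T1/2 = 0.6931 × 23.82 = 16.5 h.
- Tail = 0.1358 × 23.82 = 3.23; residual area = 3.23/(31.67 + 3.23) = 9.3%. The true value is exp(-72k) = 13.6%.
- True AUC(0-inf) = 25/0.6931 = 36.07. CL/true = 36.07/31.67 = 1.14; AUC(0-inf)/true = 34.91/36.07 = 0.968.

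**Across assumed half-lives** (residual area as SAP vs true):

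| True T1/2 (h) | SAP T1/2, no background | SAP T1/2, 1% background | Residual %, no background | Residual %, 1% background | CL/true, no background |
|---|---|---|---|---|---|
| 6 | 6.0 (-1%) | 7.3 (+22%) | 0.0 vs 0.0 | 1.1 vs 0.0 | 0.944 |
| 8 | 7.7 (-3%) | 8.7 (+9%) | 0.2 vs 0.2 | 1.2 vs 0.2 | 0.949 |
| 12 | 10.8 (-10%) | 11.3 (-6%) | 1.3 vs 1.6 | 2.2 vs 1.6 | 0.975 |
| 15 | 12.6 (-16%) | 13.0 (-14%) | 2.9 vs 3.6 | 3.7 vs 3.6 | 1.004 |
| 18 | 14.0 (-22%) | 14.3 (-20%) | 4.8 vs 6.3 | 5.5 vs 6.3 | 1.039 |
| 25 | 16.5 (-34%) | 16.7 (-33%) | 9.3 vs 13.6 | 9.8 vs 13.6 | 1.139 |
| 36 | 18.8 (-48%) | 18.9 (-47%) | 14.7 vs 25.0 | 15.1 vs 25.0 | 1.322 |

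With 1% background, T1/2 is about right at 10 h (reads 10.0) and passes -10% near 14 h. Residual area is overstated up to about 15 h and understated from about 18 h.

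**Half-life ratios.** Without background, a true ratio of 1.25 reads 1.17 (12 h), 1.12 (18 h), 1.09 (25 h) or 1.06 (36 h).

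**Power.** The spread of T1/2 shrinks with its mean. For a true ratio of 1.25 with 15% assay CV, no background and an assumed 30% between-subject SD, the standardized log difference is 0.72 (SAP) vs 0.71 (terminal slope) at 12 h, and 0.69 vs 0.62 at 25 h.

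**Does a terminal slope do better?** Simulated with 1% background subtracted, 15% assay CV and the last three quantifiable points up to 72 h. True 8, 12, 18, 25 and 36 h read medians of 8.0, 12.1, 18.0, 25.0 and 36.0 h. RMSE of log T1/2, SAP vs terminal slope: 0.09 vs 0.11, 0.07 vs 0.10, 0.23 vs 0.13, 0.41 vs 0.17 and 0.65 vs 0.26. Adding the 168 h sample cuts the last figure to 0.10 (5th-95th percentiles 31-43 h instead of 26-58 h). At 25 h it gives 0.15, with the median rising to 26.3 h.

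**The case against.** The strongest reply is that the harm is unproven and confined to secondary quantities. The documents give no half-life, and if it is 8 h or less without background the error is about 3% or smaller. Both arms use the same formula, no acceptance range attaches to these endpoints, and the formulas are printed openly. All of that stands, and it limits the weight of the point. It does not make the formulas right, and nothing elsewhere in the documents corrects them.

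The background argument is also weaker than it may look. SAP 3.3 screens on "Endogenous serum erythropoietin", but nothing says that the darbepoetin assay reads it. The 1% is an assumption, and the protocol text available is a synopsis, so its silence on assay specificity is weak evidence. Subtraction should therefore depend on what the Day 1 pre-dose samples show. It cannot simply be skipped: with 1% background left in, a noise-free slope through 24, 48 and 72 h reads 17.0, 13.7 and 14.4 h for true 6, 8 and 12 h, which is worse than the SAP.

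A reader might infer that residual area is always understated, or that T1/2 is always at least 10% off from 12 h. Both hold only without background. A reader might also infer lost power in the SAP 8.2 comparisons ("Normally distributed quantitative variables will be tested using the two-sample"). The standardized differences do not support that.

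**Conclusion.** The formulas are wrong as written. That conclusion, and the ceilings of about 25 h and about one third, follow from SAP 8.4 alone for any profile that does not rise after injection. A sustained late rise would exceed them, but is not expected after an IV injection.

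The realised error is conditional on a half-life that the documents do not give, and on mono-exponential decline. Without background it runs from about 3% at 8 h to 48% at 36 h for T1/2, with CL 14% too high at 25 h and 32% at 36 h. With 1% background it changes sign near 10 h.

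The consequence is bias in reported T1/2, k_el, residual area, AUC(0-inf) and CL. It would be tempting to conclude that the equivalence claim is compromised. The documents do not support that: the decision rule in SAP 8.2 and the protocol's Statistical Analysis section rests on AUEC(1-29), which uses none of these quantities. Sample size, AUC(0-72), Cmax and Tmax are also unaffected. This should be corrected, but it does not block the primary analysis.

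**What to change.** In SAP 8.4:

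1. If the Day 1 pre-dose samples show measurable concentration, subtract the subject's mean of those four values before items 5-11. Do not use dose-4 pre-dose values, which contain carry-over.
2. Estimate the terminal slope λz by log-linear regression on the last three or more quantifiable points. Define quantifiable and not estimable in advance, and use goodness of fit only to flag profiles. After dose 1, include the 168 h sample when quantifiable.
3. Set k_el = λz, T1/2 = ln2/λz, AUC(0-inf) = AUC to the last quantifiable point + C(last)/λz, residual area from these, MRT = AUMC(0-inf)/AUC(0-inf), and CL = Dose/AUC(0-inf) after dose 1. Label any dose-4 CL as subject to carry-over. If 168 h is the last point, bridge 72-168 h with a log trapezoid. At a true 36 h the linear rule gives 96 × (0.2500 + 0.0394)/2 = 13.9 against a true (0.2500 - 0.0394)/0.01925 = 10.9, an excess of 3.0 on a total of 51.9 (about 6%). Keep item 11's reference point of 72 h.
4. If the present quantity is kept, name it a truncated-MRT (0-72 h) half-life and show it as supplementary.
5. Reconcile the protocol's AUC0-168 label with the description beside it and with AUC(0-inf) in SAP 4.1.

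The cost is SAP wording and standard non-compartmental code. There are three downsides. λz is more variable, and some profiles may not be estimable. With 1% background the SAP formula has slightly lower RMSE at 8 and 12 h. CL does not improve at 12-15 h without background: fixed CL/true is 0.960 and 0.969, against 0.975 and 1.004 now, because of linear-trapezoid bias.

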	
 – The elimination half-life ($T_{1/2}$) – The total area under the Concentration vs. Time curve from 0 to infinity (AUC_{0-168}) – The time to maximum drug concentration in the serum (T_{max}) – The residual area – The elimination constant (k_{el}) – The total clearance (CL). 
Methods used for PK assessment: The PK analysis will include all subjects who have received all doses of the test/reference drug as per protocol. Not more than 2 PK blood collections after the first injection and not more than 2 PK blood collections after the fourth injection can be missed. Subjects who have two consecutive blood samples missed will be not included in the analysis. The PK parameters will be analyzed based on darbepoetin alfa concentrations in the subject’s serum.

PD Endpoints
	
Endpoints:
 
 • Primary endpoint: 
 — The area under the baseline-adjusted Effect vs. Time curve from injection to Day 29 after the repeated-dose IV administration of the test/reference drug ($AUEC_{(1-29)}$). • Secondary endpoints: 
 — The maximum increase in hemoglobin from baseline, estimated from injection to Day 29 after the repeated-dose IV administration of the test/reference drug ($AC-E_{max}$). 
Supplementary endpoints:
 
 — The time to the absolute maximum increase in hemoglobin from injection to Day 29 after the repeated-dose IV administration of the test/reference drug (T_{max}). 
In addition, PD parameters ($AUEC$, $AC-E_{max}$, and T_{max}) will be estimated based on the reticulocyte and RBC counts and on hematocrit values.
 
Methods used for pharmacodynamic assessment:

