### **3.2. Time Points for Blood Sampling to Evaluate PK and PD**

In this study, blood samples will be collected according to the schedule to measure the concentration of darbepoetin alfa, evaluate the hemoglobin-based PD parameters, and to evaluate additional characteristics of the red blood (reticulocytes, RBC, hematocrit). The study also involves procedures to monitor the safety.

Blood samples for darbepoetin alfa concentration will be collected before and after each IV injection of the test/reference drug.

Collections will be performed as follows:

- Visit 1 (Day 1 – Day 2): 30 min, 20 min, 10 min and immediately before the first injection of darbepoetin alfa and then 5 min, 10 min, 15 min, 20 min, 30 min, 45 min, 1 h, 2 h, 4 h, 8 h, 16 h, and 24 h after the first injection.
- Visit 2 (Day 3): 48 h after the first injection.
- Visit 3 (Day 4): 72 h after the first injection.
- Visit 5 (Day 8): immediately before the second injection.
- Visit 9 (Day 15): immediately before the third injection.
- Visit 13, (Day 22 – Day 23): 30 min, 20 min, 10 min and immediately before the fourth injection of darbepoetin alfa and then 5 min, 10 min, 15 min, 20 min, 30 min, 45 min, 1 h, 2 h, 4 h, 8 h, 16 h, and 24 h after the fourth injection.
- Visit 14 (Day 24): 48 h after the fourth injection.
- Visit 15 (Day 25): 72 h after the fourth injection.

Blood samples for PD study will be collected as follows:

- Visit 1 (Day 1 – Day 2): before the injection and 24 h (one day) after the first injection.
- Visit 3 (Day 4): 72 h (3 days) after the first injection.
- Visit 4 (Day 6): 120 h (5 days) after the first injection.
- Visit 5 (Day 8): 168 h after the first injection (immediately before the second injection).

- Visit 6 (Day 9): 192 h after the first injection (24 h after the second injection).
- Visit 7 (Day 11): 240 h after the first injection (3 days after the second injection).
- Visit 8 (Day 13): 288 h after the first injection (5 days after the second injection).
- Visit 9 (Day 15): 336 h after the first injection (immediately before the third injection).
- Visit 10 (Day 16): 360 h after the first injection (one day after the third injection).
- Visit 11 (Day 18): 408 h after the first injection (3 days after the third injection).
- Visit 12 (Day 20): 432 h after the first injection (5 days after the third injection).

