#### **4.2. Pharmacodynamics Endpoints**

- Primary endpoint:  
AUEC(1-29) (the area under effect curve) based on the change of hemoglobin level from the moment of injection to Day 29 after the repeated IV administration of the test/reference drug
- Secondary endpoints:  
AC- $E_{max}$  (the maximum increase in hemoglobin level from baseline), from the first injection to Day 29 after the repeated IV administration of the test/reference drug
- Supplementary endpoints:  
 $T_{max}$  (the time to the absolute maximum increase of hemoglobin level from injection to Day 29 after the repeated IV administration of the test/reference drug).  
In addition, PD parameters (AUEC, AC- $E_{max}$  and  $T_{max}$ ) will be estimated based on the reticulocyte and RBC counts and on hematocrit values.

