#### **6. SAMPLE SIZE CALCULATION**

The sample size was determined using the variation coefficients for hemoglobin increase (Hb AUEC) obtained by Cheung, 2001. The estimated Type I error was 5% ( $\alpha=0.05$ ) and Type II error was 20% ( $\beta=0.2$ ), with the test power of 80%.

The sample size was calculated with the “sample N.TOST” function of the “PowerTOST” package for R. The calculation used the CV values and the ratios of the mean Hb increases (AUEC).

$$CV_{AUC(Hb)}(\%) = \frac{\sigma_{AUC(Hb)}}{\bar{x}_{AUC(Hb)}} = \frac{12.92}{45.4} = 28.46\%$$

**Table 1.** Test power and sample size

Index	Mean value ratio	CV (%)	Sample size (N)	Test power
AUEC (1-29) hemoglobin	$\frac{\mu_T}{\mu_C} = 1$	28,46	N AUC(Hb)} = 56 volunteers. (28 volunteers per group)	80,95%

The study should include 28 subjects per group and 6 subjects as backups to replace potential early withdrawals (62 volunteers total).

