3.  $AUEC_{(1-29)}$  – area under effect curve from the moment of injection to the day 29 after repeated IV injections test drug/reference drug based on the hemoglobin level (reticulocytes counts, RBC, hematocrit)

$AUEC_{(1-29)}$  will be calculated as:

CONFIDENTIAL

Version 1.0 dated 10-Oct-2016

Page 16 of 17

$$AUEC_{(1-29)} = \sum_{p=2}^{16} \frac{(C_p + C_{p-1}) * (t_p - t_{p-1})}{2},$$

где  $C_p$  hemoglobin level (reticulocytes counts, RBC, hematocrit) in the time point  $t_p$  (days);

$$t_p \in \{ 0; 1; 3; 5; 7; 8; 10; 12; 14; 15; 17; 19; 21; 22; 24; 28 \}; p=1, \dots, 16$$

4. **AC-Emax** – absolute maximum increase in the test parameter vs. baseline based on the change in the hemoglobin level (absolute reticulocyte count, erythrocytes count)

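### The SAP's only AUEC(1-29) formula integrates the raw hemoglobin level, not the baseline-adjusted primary endpoint; coded as written, a product with half the effect would pass 80-125%

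*SAP*

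**What the plan says.** Three places describe an adjusted variable:

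- Protocol, PD Endpoints, primary endpoint: "The area under the baseline-adjusted" effect-time curve, to Day 29.
- SAP 4.2: AUEC(1-29) is "based on the change of hemoglobin level from the moment of injection to Day 29".
- SAP 6: "The calculation used the CV values and the ratios of the mean Hb increases (AUEC"), with SD 12.92, mean 45.4, CV 28.46%, 28 per group and power 80.95%.

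Two places describe the unadjusted level:

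- SAP 8.4, Pharmacodynamics parameters, item 3, the only formula: a trapezoid sum over 16 times from day 0 to day 28, where C_p is the "hemoglobin level (reticulocytes counts, RBC, hematocrit) in the time point" t_p. It has no baseline term, and the sentence introducing it also refers to the level.
- SAP 8.2, Quantitative Data: the variable list has "Area under effect curve «Hb level — time"».

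The next item in SAP 8.4, AC-Emax, does state its reference: "absolute maximum increase in the test parameter vs. baseline based on the change in the hemoglobin level". SAP 10 declares no deviation from the protocol's methods. AUEC(1-29) is the only parameter given an acceptance interval (90% CI within 80-125%; Protocol, Statistical Analysis, and SAP 8.2).

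**The concern.** The formula is what a programmer implements, and it computes a different variable from the one the protocol names and the study was sized on. Every participant enters with 120 to 150 g/L of hemoglobin whatever drug he receives, and the raw area counts that amount for 28 days in both arms. This pulls the test-to-reference ratio towards 1. A margin of 80-125% is a real test of the hemoglobin increase, but it tests little when applied to the level. A positive result on the raw area would then say almost nothing about whether the two products stimulate erythropoiesis equally. Leaving both versions in the plan also allows the choice to be made after the data are seen.

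**Working it through.** **1. Reproduce the plan's figure.** Inputs from SAP 6: CV = 12.92/45.4 = 28.46%, ratio 1, 28 per arm, α = 0.05 per side; limits 0.80-1.25. On the log scale σ = √ln(1 + 0.2846²) = 0.279, SE = 0.279 × √(2/28) = 0.0746, df = 54. Exact two one-sided tests power is 80.95% at 28 per arm and 79.03% at 27. The design reproduces for a variable with a CV of 28.46%.

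**2. Relate the two areas.** The intervals of the SAP 8.4 grid sum to 28 days, so

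raw area = 28 × baseline + baseline-adjusted area.

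The lowest eligible hemoglobin alone contributes 120 × 28 = 3360 g/L·day (336 g/dL·day, or 12 × 4 = 48 g/dL·week). The planning mean of 45.4 is below all of these.

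**3. Raw ratio for a product with half the effect.** Here this means half the hemoglobin rise. Let b be baseline and r the reference arm's time-averaged rise:

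raw ratio = (b + r/2)/(b + r); for an inert product, b/(b + r).

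At b = 135 g/L, the middle of the entry range:

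| r (g/L) | half effect | inert |
|---|---|---|
| 10 | 0.97 | 0.93 |
| 16.2 | 0.95 | 0.89 |
| 20 | 0.94 | 0.87 |
| 30 | 0.91 | 0.82 |

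The documents do not give r. The value 16.2 is an assumption: 45.4 read as g/dL·day gives 45.4/28 = 1.62 g/dL.

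The half-effect ratio reaches 0.80 at r = 0.2b/0.3, which is 80, 90 and 100 g/L for b = 120, 135 and 150. At b = 135 that is a mean hemoglobin of 225 g/L, against the protocol's limiting level of 180 g/L. The inert ratio falls below 0.80 once r exceeds 0.25b, which is 30, 33.75 and 37.5 g/L.

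**4. Probability of passing.** Simulation assumptions, not in the documents: entry hemoglobin uniform on 120-150 g/L, lognormal rise with CV 28.46%, 28 per arm, log-scale 90% CI, 20,000 trials per cell.

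| r (g/L) | half effect, raw | inert, raw | half effect, adjusted |
|---|---|---|---|
| 5 to 16.2 | 100% | 100% | 0% |
| 20 | 100% | 99.9% | 0% |
| 25 | 100% | 91% | 0% |
| 30 | 100% | 34% | 0% |
| 35 | 100% | 2% | 0% |
| 40 | 99.98% | about 0% | 0% |

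On the adjusted area, true ratios of 0.80 and 1.25 pass 5% of the time and a ratio of 1 passes 81%, as a calibrated test should. The raw area has a mean CV of only 6.2-8.1% in these runs, far from the planning 28.46%.

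**5. Sensitivity.**

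- Entry ranges of 120-135, 130-150 or 138-150 g/L leave the half-effect raw pass rate at 100% for rises of 5 to 40 g/L.
- The protocol's withdrawal rule at 180 g/L was applied with an assumed linear climb, whose Day 22 rise is 1.5r. It removes 3%, 11%, 28% and 47% of the reference arm at r = 16.2, 20, 25 and 30. The half-effect raw pass rate stays at least 99.9%.
- The half-effect product starts to fail only in an extreme case: b = 120 and r = 60, an average at the limit for the whole period. The ratio is then 0.833 and the pass probability 45-92% for raw CVs of 10% down to 5%.

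**The case against.** The strongest reply is that the intention is clear. The protocol, SAP 4.2 and SAP 6 all point to the adjusted variable, SAP 10 says nothing departs from the protocol, and the formula looks like the pharmacokinetic trapezoid reused with its symbol C_p. A careful programmer would subtract baseline. That is fair, and every pass rate above is conditional on literal coding. But SAP 10 does not repair the formula. It asserts agreement where there is none, and the formula is the most specific instruction on the primary variable.

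Four narrower points stand in part:

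- The documents give no dose-response relation, so the result is about half the hemoglobin rise, not half the potency in any other sense.
- The equivalence rule is worded for hemoglobin and darbepoetin alfa together. If a drug-exposure ratio were also required, a product with low exposure could fail there. The result concerns the hemoglobin criterion.
- SAP 6 gives neither units nor a time window for 45.4, so the comparison in step 2 supports the adjusted reading without proving it. The SAP's own reference to the increase is the firmer evidence.
- The 80.95% holds if the 28.46% already includes error in the baseline measurement. If error with SD 3 g/L were added on top and non-positive areas dropped, simulated power would be about 58% at a rise of 20 g/L, 45% at 16.2 and 10% at 10. This does not favour the raw area; it means the power figure is conditional on the planning CV.

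**Conclusion.** The concern holds, and the formula must be corrected before the analysis. SAP 8.4 item 3 contradicts the protocol's primary endpoint and the SAP's own definition in 4.2. Followed literally, it lets a product with half the reference's hemoglobin rise meet the hemoglobin AUEC criterion almost with certainty for time-averaged rises of 5 to 40 g/L, where the adjusted area rejects it every time. An inert product would also pass at rises up to about 20 g/L, though it does fail at large ones. The rise, its distribution and the entry hemoglobin distribution are assumptions. The half-effect conclusion barely depends on them, because a ratio of 0.80 needs a rise of 80 to 100 g/L. The stated CV and power belong to the adjusted variable as SAP 6 describes it.

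**What to change.** In SAP 8.4 item 3, replace C_p by C_p minus the subject's pre-dose Day 1 value, for hemoglobin, reticulocytes, RBC and hematocrit. Name that value as the baseline; it is the t = 0 point of the formula's own grid. Bring the variable list in SAP 8.2 into line with the protocol and SAP 4.2. State that the 90% CI and the 80-125% decision apply to the baseline-adjusted hemoglobin AUEC(1-29), with any raw area descriptive only.

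Two details follow from adjusting and should be fixed before unblinding:

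- **Ratio scale.** The log scale (geometric mean ratio) reproduces the stated 80.95%; an arithmetic-mean ratio gives a simulated 78.1%.
- **Non-positive areas.** Keep net, signed areas and state how a value at or below zero is handled, since it has no logarithm. No subject should be excluded for that reason without such a rule. With an assumed baseline error SD of 3 g/L, the chance of at least one such value among 56 subjects is 0.8% at a rise of 16.2 g/L, 22% at 10 and 98% at 5.

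The cost is SAP wording and one line of code. The needed sample is already scheduled at Visit 1 in SAP 3.2 ("before the injection and 24 h (one day) after the first injection"). The correction itself does not change N = 56, whose 80.95% power was calculated with the CV of the increase.
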